4.2.2 Safety

The following terms are generally used in safety tables:

- AE: Adverse event includes immediate, solicited, and unsolicited (including non-serious and serious adverse events)
- Adverse Event of Special Interest (AESI): Is one of scientific and medical concern specific to the Sponsor's product or program, for which ongoing monitoring and rapid communication by the investigator to the sponsor can be appropriate. The following AESIs have been defined for VYF02 based upon the prior experience with YF vaccines:
 - Serious hypersensitivity/allergic reactions
 - Organ failure/serious viscerotropic events
 - Serious neurologic events
- Adverse Reaction (AR): Corresponds to related AE to the study vaccine, unless otherwise specified.
- Immediate: Unsolicited systemic AE checked "Yes" in the field of "immediate (within 30 minutes from the vaccination)" by the investigator in the case report form (CRF).

- Medically-Attended Adverse Event (MAAE): New onset or a worsen of a condition that prompts the participant or participant's parent/guardian to seek unplanned medical advice at a physician's office or Emergency Department.
- Solicited reaction: Event pre-listed in the CRF, and which occurred during the solicited period
- Unsolicited AE: AE recorded in the CRF as Unsolicited Systemic Events or Unsolicited Injection Site Reactions.
- Unsolicited injection site reactions are to be considered as related to the vaccine injection and therefore analyzed as ARs.
- Unsolicited AEs occurring before or after the defined period will be presented in a separate listing.
- SAE: Unsolicited AE considered serious by the investigator (reconciled with Global Pharmacovigilance database).
- Biological safety results (biochemistry and hematology for subset of subjects only): Hematology and biochemistry out-of-range test results will be summarized at D01 and D11 for participants in the subset.

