Immediate events are recorded to capture medically relevant unsolicited systemic AEs which occur within the first 30 minutes after vaccination.

Reactogenicity / Solicited Reactions

The **reactogenicity** of a vaccine refers to the property of such vaccine to be able to produce common "expected" adverse reactions (either systemic or at the injection site) and its associated signs and symptoms.

A solicited reaction is an "expected" adverse reaction (sign or symptom) observed and reported under the conditions (nature and onset) pre-listed in the protocol and CRF (eg, injection site pain or headache occurring between the day of vaccination and the next 7 days).

By definition, solicited reactions are considered as being related to the corresponding IMP administered.

For injectable vaccines, solicited reactions can either be solicited injection/administration site reactions or solicited systemic reactions.

Injection / Administration Site Reactions:

An injection/administration site reaction is an AR at and around the injection/administration site of the IMP. Injection/administration site reactions are commonly inflammatory reactions.

Solicited injection / administration site reactions are reactions at and around the injection / administration site of the IMP observed and reported under the conditions (nature and onset) pre-listed in the protocol and CRF. It is considered by default as being related to the IMP administered at that site.

Note: « Administration site reaction » term is only to be used for vaccines that are not intended to be administered by injection.

Systemic AR:

Systemic ARs are all ARs that are not injection or administration site reactions. They therefore include systemic manifestations such as headache, fever, as well as localized or topical manifestations that are not associated with the injection or administration site (eg, erythema that is localized but that is not occurring at the injection site).

Solicited systemic reactions are systemic AEs observed and reported under the conditions (nature and onset) pre-listed in the protocol and CRF. Solicited systemic reactions occurring

during the specified collection period are always considered related to the IMP even if there is evidence of alternative etiology.

Unsolicited AE/AR

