An unsolicited AE is an observed AE that does not fulfill the conditions of solicited reactions, ie, pre-listed in the CRF in terms of diagnosis and onset window post-vaccination. For example, varicella or a solicited term such as headache starting after the solicited observation period (eg, headache starting on Day 10 post-vaccination in the case where headache occurring between the day of vaccination and the next 7 days is pre-listed in the protocol and CRF as a solicited reaction).

An unsolicited AR is an unsolicited AE that is considered related to an IMP.

Unsolicited AEs includes both serious (SAEs) and non-serious unsolicited AEs.

All unsolicited AEs occurring at and around the IMP injection/administration site are to be considered by default as related to the IMP administered at that site and are therefore referred as unsolicited injection/administration site ARs.

All unsolicited AEs which are not at and around the IMP injection/administration site, are referred as systemic unsolicited AE. For each unsolicited systemic AE, the Investigator assesses the relationship to the IMP. Systemic AEs assessed as related to IMP are referred as systemic ARs.

Note: any AEs at and around the NIMP injection / administration site regardless of its nature and onset is to be reported as unsolicited systemic AE since it does not occur at and around the IMP injection/administration site.

Adverse Event of Special Interest (AESI):

An adverse event of special interest (serious or non-serious) is one of scientific and medical concern specific to the Sponsor's study intervention or program, for which ongoing monitoring and rapid communication by the Investigator to the Sponsor can be appropriate. Such an event might warrant further investigation in order to characterize and understand it. Depending on the nature of the event, rapid communication by the study Sponsor to other parties (eg, regulators) might also be warranted.

For more detailed instructions on safety data collection, refer to the Sanofi Pasteur Safety Guideline.

Medically Attended AE (MAAE)

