10.3.2 Definition of SAE

An SAE is defined as any adverse event that, at any dose:

a. Results in death

b. Is life-threatening

The term 'life-threatening' in the definition of 'serious' refers to an event in which the participant was at risk of death at the time of the event. It does not refer to an event, which hypothetically might have caused death, if it were more severe.

c. Requires inpatient hospitalization or prolongation of existing hospitalization

- In general, hospitalization signifies that the participant has been admitted (usually involving at least an overnight stay) at the hospital or emergency ward for observation and/or treatment that would not have been appropriate in the physician's office or outpatient setting. Complications that occur during hospitalization are AEs. If a complication prolongs hospitalization or fulfills any other serious criteria, the event is serious. When in doubt as to whether "hospitalization" occurred or was necessary, the AE should be considered serious.
- Hospitalization for elective treatment of a pre-existing condition that did not worsen from baseline is not considered an AE.

d. Results in persistent or significant disability/incapacity

- The term disability means a substantial disruption of a person's ability to conduct normal life functions.
- This definition is not intended to include experiences of relatively minor medical significance such as uncomplicated headache, nausea, vomiting, diarrhea, influenza, and accidental trauma (eg, sprained ankle) which may interfere with or prevent everyday life functions but do not constitute a substantial disruption.

e. Is a congenital anomaly/birth defect

f. Is other medically important event

- The term "Other medically important events" refers to events which do not meet any of the above seriousness criteria, but which are considered as serious based on Investigator medical judgment
- Medical or scientific judgment should be exercised by the Investigator in deciding whether
 expedited reporting is appropriate in other situations such as significant medical events that
 may not be immediately life-threatening or result in death or hospitalization but may

- jeopardize the health of the participant or may require intervention to prevent one of the other outcomes listed in the above definition. These important medical events should also usually be considered serious.
- Examples of such events include invasive or malignant cancers, intensive treatment in an

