4.2.2.4 SAEs

An event will be considered as a serious event if "Yes" is checked for "Serious" in the CRF.

SAEs will be analyzed throughout the study using the following periods:

- Within 28 days after a vaccination
- During the period from 29 days after the vaccination until the last participant contact at M6
- During the study for related SAEs (ie, all related SAEs occurred during the study)

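### The SAP has two SAE counting rules that disagree, so it is unclear whether a serious solicited reaction, related by definition, enters the SAE and related-SAE rows

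*SAP*

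**What the plan says.** SAP 4.2.2 lists the terms generally used in the safety tables. Its AE entry includes solicited events, but its SAE entry is narrower: "SAE: Unsolicited AE considered serious by the investigator", with reconciliation against the pharmacovigilance database added in brackets. The same list defines an unsolicited AE by where it is entered: "AE recorded in the CRF as Unsolicited Systemic Events or Unsolicited Injection Site Reactions".

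SAP 4.2.2.4, which sets the SAE analysis periods, has no such limit. It begins "An event will be considered as a serious event if" and the only condition that follows is a Yes in the CRF's Serious field. One of its periods takes all related SAEs during the study.

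Protocol 10.3.2 is also unrestricted: "An SAE is defined as any adverse event that, at any dose", followed by the seriousness criteria. Protocol 10.3.1 keeps the two kinds of event apart: "An unsolicited AE is an observed AE that does not fulfill the conditions of solicited reactions". It also says that solicited systemic reactions in their collection period are "always considered related to the IMP even if there is evidence of alternative etiology"; solicited injection site reactions are related by default.

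Protocol 8.3.1 sets the solicited periods at D01 to D08 for injection site reactions and D01 to D15 for systemic reactions. Tables 10.1 and 10.2 list the terms: pain, erythema and swelling; fever, headache, malaise and myalgia.

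**The concern.** A participant admitted to hospital with a fever that starts inside the solicited window, with no further diagnosis, has an SAE under protocol 10.3.2. That event is a solicited reaction and so, by protocol 10.3.1, not an unsolicited AE. A programmer who follows the SAP 4.2.2 term would not count it as an SAE; one who follows SAP 4.2.2.4 would.

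Every event affected is related by definition. Related SAEs up to 5 years are part of a stated secondary safety endpoint (protocol Section 3, SAP 4.1). At the low counts to be expected, one event can decide whether the report says that there were no related SAEs in an arm. The literal 4.2.2 rule can only remove events, so any error would understate related harm.

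**Working it through.** **Definitions side by side, for a serious solicited reaction**

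| Place | Rule | Is it an SAE? |
|---|---|---|
| Protocol 10.3.2 | Any adverse event meeting a seriousness criterion | Yes |
| SAP 4.2.2 | Unsolicited AE judged serious, reconciled with the pharmacovigilance database | No, if recorded only as solicited |
| SAP 4.2.2.4 | Any event with Serious ticked | Yes, if the field exists on that form and is ticked |

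**Would another table row show it?**

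- The solicited rows of SAP Tables 7.8 and 7.9 show any reaction and, in 7.9, Grade 3 reactions. They do not show seriousness, and protocol 10.3.2 says that serious and severe are different things.
- The protocol's MAAE definition (10.3.1) excludes solicited reactions, so the MAAE rows are not a dependable backstop.
- The SAE and Related SAE rows of Table 7.8 carry no unsolicited qualifier. They neither exclude the event nor settle which definition feeds them.
- SAP 4.2.2.7.6, on discontinuation, names solicited and unsolicited AEs as two sources. The SAE sections do not.

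**Size, for illustration only.** The plan states no SAE rate, so there is no figure to reproduce. Inputs:

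- Planned group sizes of 380 (vYF) and 190 (YF-VAX), from protocol 9.2 and SAP 5.5, used as the safety denominators.
- The exact (Clopper-Pearson) 95% interval specified in SAP 5.1.2.2.
- An assumed count of 0 to 2 serious solicited reactions per arm, because the documents give none.

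For x events in n, the lower limit is the 0.025 quantile of Beta(x, n − x + 1) and the upper limit is the 0.975 quantile of Beta(x + 1, n − x). For x = 0 the lower limit is 0 and the upper limit reduces to 1 − 0.025^(1/n):

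- n = 380: 1 − 0.025^(1/380) = 0.97%
- n = 190: 1 − 0.025^(1/190) = 1.92%

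| Events | vYF, n = 380 | YF-VAX, n = 190 |
|---|---|---|
| 0 | 0% (0 to 0.97%) | 0% (0 to 1.92%) |
| 1 | 0.26% (0.01 to 1.46%) | 0.53% (0.01 to 2.90%) |
| 2 | 0.53% (0.06 to 1.89%) | 1.05% (0.13 to 3.75%) |

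If a single vYF event is dropped, the upper limit falls from 1.46% to 0.97%, a relative fall of (1.46 − 0.97)/1.46 = 34%.

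**The case against.** A reader might infer that the SAP counts an SAE only if it is unsolicited, so that serious solicited reactions are certain to be missing from the rates. The documents do not support that.

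- SAP 4.2.2.4 is the section devoted to SAEs, and its rule is unrestricted. SAP 4.2.2 is a list of terms.
- The 4.2.2 term includes reconciliation with the pharmacovigilance database, and protocol 8.3.1 requires every SAE to reach the sponsor within 24 hours. A serious event known only from the solicited pages should surface there.
- The SAP defines an unsolicited AE by the CRF form used. If sites enter a serious fever on the unsolicited page, it meets both SAP wordings and nothing is lost. The documents do not say which form applies.
- Protocol 10.3.3 asks for a diagnosis rather than symptoms where possible, and protocol 10.3.6 has YEL-AVD and YEL-AND reported as SAEs. Many serious events would therefore carry a term outside the solicited lists.
- Protocol 10.3.1 itself says that unsolicited AEs comprise serious and non-serious ones, so the SAP wording has some root in the protocol.

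Most of this stands, and it makes omission a risk rather than a fact. It does not remove the conflict. That unsolicited AEs can be serious does not mean that every SAE is unsolicited, and protocol 10.3.2 has no such limit. The reconciliation clause qualifies a set already restricted to unsolicited AEs; it does not say that a serious solicited reaction is added. SAP 4.2.2.4 can be read as only explaining how the investigator's judgement of seriousness is captured, which leaves the 4.2.2 restriction in force. What remains is the serious event with no diagnosis beyond a listed term, and for that case the SAP gives two answers.

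**Conclusion.** The point holds as an inconsistency within the SAP, and between SAP 4.2.2 and protocol 10.3.2. The handling of a serious solicited reaction is not settled: 4.2.2 could leave it out of the SAE and Related SAE rows, while 4.2.2.4 counts it. It cannot be concluded that any related SAE is in fact lost.

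The effect is limited to descriptive safety rates; the primary analysis, alpha and sample size are untouched. One such event in the vYF arm would be the difference between 0.26% and 0%. That figure rests on an assumed event count and on planned group sizes, and the true number of such events may be zero. The correction is worth making because the conflict is plain, any error would run only towards understating related SAEs, and removing it costs almost nothing.

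**What to change.** 1. In SAP 4.2.2, reword the SAE term to say: *any AE, solicited or unsolicited, that the investigator considers serious, reconciled with the Global Pharmacovigilance database*. This agrees with SAP 4.2.2.4 and protocol 10.3.2.
2. State the CRF form on which a serious solicited reaction is recorded, and confirm that a Serious field is available there. Rewording alone may leave the programmer without a variable to use.
3. In Table 7.8, count such an event once per participant in the SAE and Related SAE rows, with relationship set to related, and keep it in the solicited tables too.

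The cost is a sentence or two in the SAP and a small programming check. SAE rates can only stay the same or rise slightly.

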4.2.2.1 Solicited Reactions

Solicited injection site reaction will be collected within 7 days after vaccination.

Solicited systemic reactions will be collected within 14 days after vaccination.

4.2.2.1.1 Daily Intensity

All daily records for solicited reactions will be derived into daily intensity according to the following classification: None, Grade 1, Grade 2, Grade 3, or Missing (Unknown).

For measurable injection site reactions:

- None: > 0 to < 25 mm
- Grade $1: \ge 25$ to ≤ 50 mm
- Grade $2: \ge 51$ to ≤ 100 mm
- Grade 3: > 100 mm

For Fever:

- None: $< 38.0^{\circ}$ C or $< 100.4^{\circ}$ F
- Grade $1: \ge 38.0^{\circ}$ C to $\le 38.4^{\circ}$ C or $\ge 100.4^{\circ}$ F to $\le 101.1^{\circ}$ F
- Grade 2: \geq 38.5°C to \leq 38.9°C or \geq 101.2°F to \leq 102.0°F
- Grade $3: \ge 39.0^{\circ}$ C or $\ge 102.1^{\circ}$ F

For the derivation of daily intensities, the following sequential steps will be applied:

- 1) Solicited reactions (except Fever/Pyrexia) with CRF presence recorded as "No" and with all daily records missing (Unknown) then all daily intensities will be derived as None.
- 2) For non-measurable solicited reactions, daily intensities will correspond to daily records reported in the clinical database. For measurable solicited reactions the daily measurements reported in the clinical database will be converted based upon the intensity scales defined in the protocol; this assumes a reaction that is too large to measure (non-measurable, "NM") is Grade 3. Note the intensity could be considered "None" (not a reaction) in the analysis despite being considered a reaction by the investigator (eg, swelling measurement > 0 mm but < 25 mm in adults).

Note: The maximum intensity on the ongoing period is derived from the record of the maximum intensity/measurement after the end of the solicited period following the rule described above.

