8.3.2 Method of Detecting AEs and SAEs

Individual Diary cards (DCs), specifically designed for this study by the Sponsor and provided to the study sites, will be given to study participants for the recording of daily safety information.

These diary cards will include pre-listed terms and intensity scales as well as areas for free text to capture additional safety information or other relevant details. Participants will also be provided with rulers for measuring the size of injection site reactions, and with standard digital thermometers for measuring daily temperatures. To ensure consistency of reporting, the study sites will instruct participants on how to correctly use these tools.

At specified intervals, the Investigator or an authorized designee will interview the participants to collect the information recorded in the diary card or memory aid and will attempt to clarify anything that is incomplete or unclear. All clinical study information gathered by the study site will be reported electronically by the Investigator or authorized designee using a web based CRF. Any information that was not documented in the diary card will first be captured in the source document and then reported electronically.

The 6-month follow-up will be done by interviewing participants either during a visit or over the telephone using a questionnaire to capture SAEs and serious AESIs, if applicable.

The method of recording, evaluating, and assessing causal relationship of AE and SAE and the procedures for completing and transmitting SAE reports are provided in Appendix 10.3.

Care will be taken not to introduce bias when detecting AEs and/or SAEs. Open-ended and non-leading verbal questioning of the participant is the preferred method to inquire about AE occurrences.

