4.2.2.1.2 Maximum Overall Intensity

Maximum overall intensity is derived from the daily intensities computed as described in Section 4.2.2.1.1 and is calculated as the maximum of the daily intensities over the period considered.

Note: The maximum intensity could be considered "None" (not a reaction) in the analysis despite being considered a reaction by the investigator (eg, swelling measurement > 0 mm but < 25 mm in adults).

4.2.2.1.3 **Presence**

Presence is derived from the maximum overall intensity over the time period considered:

- None: No presence
- Grade 1, Grade 2, or Grade 3: Presence
- Missing or Unknown: Missing presence

Participants with at least one non-missing presence for a specific endpoint will be included in the analysis. Conversely, those without a non-missing presence will not be included in the analysis of the endpoint.

The time period is displayed as follows:

- Injection site reactions: D1-D4, D5-D8, D9 or later
- Systemic reactions: D1-D4, D5-D8, D9-D15, D16 or later.

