4.2.2.7.6 Adverse Events Leading to Study Discontinuation

This information will be summarized as collected. A flag is available in the clinical database for all AEs in order to identify AEs leading to discontinuation before the end of active phase.

In general, the items that are counted are:

- Disposition table: A participant who, on the "Completion at End of Study" form question "What was the participant's status?" has "Adverse Event" checked.
- Safety overview table: A participant who has either on the "Completion at End of Study" form, question" What was the participant's status?" has "Adverse Event" checked or lists a solicited AE that has "Caused Study Termination" checked that is at least Grade 1 or an unsolicited AE that has "Caused Study Discontinuation" checked that is at least Grade 1 or missing and is within the time period indicated.

System Organ Class (SOC)/Preferred Term (PT) table: A solicited AE that has "Caused Study Termination" checked that is at least Grade 1 or an unsolicited AE that has "Caused Study Discontinuation" checked that is at least Grade 1 or missing and is within the time period indicated.

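### SAP 4.2.2.1.1 uses the CRF presence field in one direction only: 'No' without daily records counts as no reaction, 'Yes' without daily grades leaves the endpoint, so rates of pain, headache, malaise and myalgia fall whenever such records exist

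*SAP*

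**What the plan says.** SAP 4.2.2.1.1 derives daily intensities in two sequential steps.

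- Step 1 covers every solicited reaction except fever. Where CRF presence is 'No' "and with all daily records missing (Unknown) then all daily intensities will be derived as None".
- Step 2 covers what remains: "For non-measurable solicited reactions, daily intensities will correspond to daily records reported in the clinical database". Measurable reactions are graded from the recorded measurement, with a caution: "Note the intensity could be considered 'None' (not a reaction) in the analysis despite being considered a reaction by the investigator". The example given is a swelling below 25 mm.

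SAP 4.2.2.1.2 takes the maximum of the daily intensities, without saying how Missing days enter it. SAP 4.2.2.1.3 maps a missing maximum to missing presence and sets the denominator: "Participants with at least one non-missing presence for a specific endpoint will be included in the analysis". The exclusion is then spelled out as the other side of that rule: "Conversely, those without a non-missing presence will not be included in the analysis of the endpoint". The table shells define M as participants with data available for the endpoint.

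The missing-data sections add no rule for 'Yes'. SAP 5.3.2 says that safety data are generally not replaced, and 5.3.2.4 refers back to 4.2.2.1.1.

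SAP 4.2.2.7.6 treats solicited and unsolicited events differently for study discontinuation. A solicited AE counts if its termination flag is "checked that is at least Grade 1 or an unsolicited AE that has" the corresponding flag; only the unsolicited half goes on to admit a missing grade.

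**The concern.** Among participants without daily records for a reaction, a reported absence is kept and a reported presence is removed. Exclusion then depends on the outcome being estimated.

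This differs from how the SAP treats incomplete safety data elsewhere. An unsolicited AE counts if it has a verbatim term and is not Grade 0 (4.2.2.2.1), and a missing grade simply stays missing (5.3.2.4). An ungraded unsolicited headache is therefore counted, while an ungraded solicited headache is not. A missing causal relationship is read as related (5.3.2.2). The definition of a solicited reaction in 4.2.2 asks that the event be pre-listed and occur in the solicited period; it does not ask for a grade.

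At stake is the secondary objective of describing the safety profile of vYF beside that of YF-VAX, which Tables 7.8 and 7.9 serve directly.

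**Working it through.** **Inputs.** Group sizes are 380 (vYF) and 190 (YF-VAX), from Protocol 9.2 and SAP 5.5. The documents give no reaction rate and no share of reactors with 'Yes' but no daily grade. Both are assumed below: rates of 10% to 50%, shares of 2% to 20%. The plan has no figure of its own to reproduce.

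**1. Trace a non-measurable reaction with no daily records.**

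| CRF presence | Daily intensity | Presence | Effect on n/M |
|---|---|---|---|
| 'No' | None (step 1) | No presence | in M, not in n |
| 'Yes' | Missing (step 2) | Missing | out of both |
| blank | Missing (step 2) | Missing | out of both |

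**2. Direction.** Let N be participants, R true reactors, and y reactors with 'Yes' but no grade. The rate with every 'Yes' counted is R/N; the SAP rate is (R − y)/(N − y). Cross-multiplying, (R − y)/(N − y) < R/N is equivalent to Ny > Ry, which holds whenever y > 0 and R < N. For the four non-measurable reactions the shift is therefore downward.

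**3. Size, N = 380, assumed true rate 30% (R = 114).**

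| Share ungraded | y | SAP rate |
|---|---|---|
| 2% | 2 | 112/378 = 29.6% |
| 5% | 6 | 108/374 = 28.9% |
| 10% | 11 | 103/369 = 27.9% |
| 20% | 23 | 91/357 = 25.5% |

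The Clopper-Pearson 95% CI for 114/380 is 25.4% to 34.9%, so the 10% case lies inside it. At 10% ungraded, a true rate of 10% becomes 34/376 = 9.0%, and 50% becomes 171/361 = 47.4%.

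**4. Between arms, true rate 30% in both.** In YF-VAX, R = 57 and 10% ungraded is y = 6, giving 51/184 = 27.7%.

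- 10% in both arms: 27.9 − 27.7, a shift of about 0.2 points. Even this comes from rounding y to whole participants; with exactly equal shares both rates are 0.27/0.97 = 27.8%.
- vYF only: 27.9 − 30.0 = −2.1 points.
- YF-VAX only: 30.0 − 27.7 = +2.3 points.

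**5. Erythema and swelling.** Here 'Yes' may be an event under 25 mm, which the SAP grades None. Let q be the share of the y ungraded records that truly reached 25 mm, and r the graded reactors. The true rate is (r + qy)/N against the SAP's r/(N − y). With r = 38, y = 12, N = 380, the SAP rate is 38/368 = 10.33%:

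| q | True rate | SAP minus true |
|---|---|---|
| 0 | 10.00% | +0.33 points |
| 0.10 | 10.32% | about 0 |
| 0.50 | 11.58% | −1.25 points |
| 1 | 13.16% | −2.83 points |

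The error is downward only when q exceeds the observed rate.

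**6. Fever.** Step 1 exempts it. Without temperatures, 'No' and 'Yes' both stay missing.

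**7. Maximum and composites.** Take a participant with headache 'Yes' ungraded, malaise and myalgia 'No', and no fever recorded. If the maximum skips Missing components, the composite is None and the participant counts as having no solicited systemic reaction; if it does not, presence is missing. The SAP does not say which. The same doubt applies to one reaction with some days None and the rest missing. If Missing is skipped, the 10% case in step 3 becomes 103/380 = 27.1%. In a composite row, only participants with no graded reaction at all are exposed, because any one graded component keeps them in the numerator.

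**The case against.** The strongest reply is that such records should be rare. Protocol 8.3.2 has the site interview participants about incomplete diary entries, Protocol 10.3.5 requires an intensity grade for each AE, and SAP 5.6 describes a data review before lock. The interview provision, "Any information that was not documented in the diary card will first be captured in the source document and then reported electronically", is there to recover information, not to license an ungraded 'Yes'. This stands: it shows that such records can arise, not that they will be common. It does not supply an analysis rule for those that remain.

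It can also be said that safety is descriptive (Protocol 9.4.2, SAP 5.1.2.1), that participants and safety assessors are blinded, and that n/M makes exclusions visible. The first two stand and limit the consequence. The third helps only partly, because M does not separate an ungraded 'Yes' from a blank form.

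Four stronger readings are tempting, and the documents do not support them.

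- That all solicited rates are biased downward: steps 5 and 6 rule this out.
- That only reactors are removed: a blank presence field is removed too.
- That composite rates fall by the full single-reaction ungraded share: a composite reactor is lost only if every reported reaction is ungraded.
- That the safety overview misses participants who left because of an ungraded solicited AE: SAP 4.2.2.7.6 also counts anyone whose end-of-study status is 'Adverse Event'.

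**Conclusion.** The one-directional rule is in the SAP, and no other section offsets it. For injection site pain, headache, malaise and myalgia, any 'Yes' record without daily grades lowers the reported rate. Whether the trial's rates will be biased cannot be settled from the documents, because the number of such records is not given. Under the assumptions above, with 2% to 10% of reactors ungraded and true rates of 10% to 50%, dropping them costs about 0.2 to 2.8 points in an arm (cells with at least one ungraded reactor). The between-arm difference is nearly unchanged if the shares and true rates are equal, and moves by about 2 points at a 30% rate if a 10% share occurs in one arm only. Nothing in the documents suggests that completion will differ by arm.

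The treatment of Missing in the maximum is a separate gap: ungraded reactors may be counted as non-reactors, but the text does not establish that they will be. The discontinuation wording matters mainly for the SOC/PT table. This is a cheap improvement to descriptive safety tables; the non-inferiority test does not use these data.

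**What to change.** - **SAP 4.2.2.1.1 and 4.2.2.1.3.** For injection site pain, headache, malaise and myalgia, treat CRF 'Yes' with no daily grade of 1 or more and at least one missing day as present with grade missing, in single-reaction and composite rows.
- **SAP 4.2.2.1.2.** State how the maximum treats Missing days and components, and that neither a maximum nor a composite can be None when a component is 'Yes' but ungraded.
- **Erythema, swelling and fever.** Keep an ungraded 'Yes' as missing in the main table, and add a sensitivity row counting it as present.
- **Reporting.** Give the number of ungraded 'Yes' records per arm.
- **SAP 4.2.2.7.6.** Count flagged solicited AEs of at least Grade 1 or missing grade, as is done for unsolicited AEs.

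The cost is a few lines of SAP text and derivation code, using a CRF field already collected. Descriptive rates may become slightly less favourable, and a small grade-missing row appears. If no such records exist, the rates do not change.
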